7.3.2. Subgroup Analyses for Primary Efficacy Endpoint

Subgroup analysis will be performed based on the following participant characteristics and baseline variables for those participants whose data are available:

- Skin type (Fitzpatrick scale Type I and II vs Type III, IV, V, VI)
- Age (12 to 17, \geq 18 to 64, \geq 65 years; \leq 40, $>$ 40 years)
- Region (North America, Europe)
- Sex (Male, Female)
- Race
- F-BSA ($<$ 1.5, \geq 1.5)

7.3.3. Sensitivity and Supportive Analyses for Primary Endpoint

7.3.3.1. Nonresponder Imputation

Nonresponder imputation will be used as an alternative method to handle missing data. All participants who do not respond, as well as all participants who are missing postbaseline values, will be defined as nonresponders for the NRI analysis.

7.3.3.2. Last Observation Carried Forward

For the participants who are missing postbaseline values, the last observed nonmissing postbaseline value will be used to fill in missing values at Week 24. Then the proposed exact logistic regression described in Section 7.3.1 will also applied to the imputed dataset.

7.3.3.3. Tipping Point Analysis

A tipping point sensitivity analysis will be conducted to examine the potential effects of missing data. The missing F-VASI75 response at Week 24 in each treatment group will be replaced by a range of values from the most conservative case to the most aggressive case. The most conservative case is that all the missing participants in 1.5% BID group are nonresponders and all the missing participants in vehicle group are responders, while the most aggressive case is the other way around. For each scenario, between-treatment comparisons will be performed using a Fisher's exact test.

7.4. Analysis of the Key Secondary Efficacy Parameters

If the primary objective is achieved, the statistical hypotheses for the following key secondary endpoints will be tested in a fixed sequence in the following order:

- F-VASI50 at Week 24
- F-VASI90 at Week 24
- T-VASI50 at Week 24
- Vitiligo – VNS Response at Week 24
- Percentage change from baseline in F-BSA at Week 24.

Key secondary efficacy analyses at Week 24 will be conducted in the FAS population. The statistical comparisons for binary outcomes (F-VASI50/90, T-VASI50, and VNS response) will be analyzed using the similar method as specified in the primary analysis.

For F-BSA, the missing values at Week 24 will be imputed using the MI method specified in the primary analysis. Then the derived percentage change from baseline in F-BSA at Week 24 will be analyzed using an ANCOVA model with treatment group, stratification factors, and baseline value as covariates. A test for superiority between ruxolitinib cream 1.5% BID and vehicle cream will be performed using the least squares mean estimate of the percentage change from baseline in F-BSA at Week 24 from the ANCOVA model. Superiority will be established if the p-value of the difference (ruxolitinib cream 1.5% BID minus vehicle) is < 0.05.

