3.2. Control of Type I Error

The gatekeeping testing strategy for the primary and key secondary analyses will be implemented to control the overall Type I error rate, 2-sided $\alpha = 0.05$. These endpoints will be tested in a fixed sequence at 2-sided $\alpha = 0.05$ level in the following order:

- Proportion of participants achieving F-VASI75 at Week 24
- Proportion of participants achieving F-VASI50 at Week 24
- Proportion of participants achieving F-VASI90 at Week 24
- Proportion of participants achieving T-VASI50 at Week 24
- Vitiligo – VNS Response at Week 24
- Percentage change from baseline in F-BSA at Week 24

The endpoint will be tested only if the primary endpoint (and the secondary endpoints in previous steps) are rejected.

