3.3. Sample Size Considerations

Approximately 300 participants will be randomized 2:1 to ruxolitinib cream 1.5% BID or vehicle and stratified by baseline skin type (Fitzpatrick scale Type I and II vs Type III, IV, V, and VI) and region (North America or Europe). The sample size is calculated to provide sufficient power ($> 85\%$) to detect a difference between the 1.5% BID with the vehicle in primary and key secondary endpoints. The powers for different endpoints are provided in [Table 2](#). The Fisher's exact test with a 2-sided alpha of 0.05 is used to provide a conservative evaluation of statistical power, and it is accurate when there is a small expected number of responders in the vehicle group.

Table 2: Powering for Primary and Key Secondary Endpoints

Endpoints	Response Rates in Ruxolitinib 1.5% BID ^a	Response Rates in Vehicle ^a	Power ^b
F-VASI75 at Week 24	20%	5%	95%
F-VASI50 at Week 24	30%	10%	95%
F-VASI90 at Week 24	10%	1%	88%
T-VASI50 at Week 24	10%	1%	88%
Vitiligo - VNS Response at Week 24	10%	1%	88%

^a Based on the results from a Phase 2, randomized, dose-ranging study (INCB18424-211).

^b Based on the Fisher's exact test with a 2-sided alpha of 0.05.

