4.1.4. Handling of Missing and Incomplete Data

For response endpoints, including F-VASI75, F-VASI50, F-VASI90, T-VASI50, and VNS 4 or 5 as listed in the primary and key secondary endpoints, all participants who are missing postbaseline values, will be handled using MI under the missing-at-random assumption.

For continuous endpoints, any participant who is missing postbaseline values may have missing data handled using MMRM or MI under the missing-at-random assumption. MMRM model implicitly adjusts for missing data through a variance-covariance structure.

For other endpoints, missing observations will be handled as detailed in the specific sections addressing each analysis.

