5.3. Analysis Populations

5.3.1. Full Analysis Set

All participants who are randomized and have baseline and any postbaseline assessments constitute the FAS. Treatment groups for this population will be defined according to the treatment assignment at the time of randomization regardless of the actual study treatment the participant might apply during his/her participation in the study. Those participants who have only study baseline, but not any postbaseline assessment are not included in the FAS.

The FAS will be used for the summary of analyses of demographics, baseline characteristics, participant disposition, and all efficacy data.

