7.2.5.1. Vitiligo Noticeability Scale

The VNS is a patient-reported measure of vitiligo treatment success, which has a 5-point scale ([Batchelor et al 2016](#)). The baseline facial photograph will be shown to the participants for reference, and a mirror will be provided for the participants to assess the vitiligo on their face. The participant will be asked to respond to the following query:

Compared with before treatment, how noticeable is the vitiligo now? Responses: (1) More noticeable, (2) As noticeable, (3) Slightly less noticeable, (4) A lot less noticeable, and (5) No longer noticeable.

VNS scores of 4 or 5 can be interpreted as representing treatment success.

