7.3.1. Primary Efficacy Analyses

The primary analysis will be based on the FAS population. The primary alternative hypothesis (superiority of ruxolitinib 1.5% BID compared with vehicle) will be tested using exact logistic regression (Mehta and Patel 1995). This model will include the treatment group (1.5% BID and vehicle) and stratification factors (skin type and region). The unadjusted p-values between each treatment group versus vehicle will be compared with the procedure defined in Section 3.2.

Odds ratio in response rates (ruxolitinib cream vs vehicle) at Week 24 will also be computed. All participants who are missing the F-VASI assessment at a given visit in the DB period will be handled using MI under the missing-at-random assumption. Rescue therapy is not allowed in the studies. Any participant who received rescue therapy will be considered as a protocol violation and will be imputed as a nonresponder. The numerical values for F-VASI will not be included in the MI model or other sensitivity analyses.

For MI, a fully conditional specification method (van Buuren 2007) that assumes the existence of a joint distribution for all variables will be used to impute F-VASI score. A regression model including treatment group, stratification factors, and baseline and postbaseline F-VASI scores up to Week 24 will be specified for the fully conditional specification method. The randomization seed will set to be 18424306 for Study INCB 18424-306 and 18424307 for Study INCB 18424-307. The imputation will be repeated 10 times to generate corresponding complete datasets, in order to reflect the uncertainty around the true value. After the missing values have been imputed, the binary variable F-VASI75 response will be derived. The exact logistic regression will be applied to each imputed dataset, and then the results will be combined for the inference.

The following is example SAS code for MI:

```
proc mi data=mi_wide seed=18424306 n impute=10 out=impute_fvasi;
  class trt01p strat1 strat2;
  var trt01p strat1 strat2 avalBASELINE avalWEEK4 avalWEEK8
  avalWEEK12 avalWEEK18 avalWEEK24;
  fcs;
run;
```

The following is example SAS code for exact logistic regression:

```
proc logistic data=fvasi75_mi exactonly;
  class trt01p (ref='VEHICLE CREAM') strat1 strat2/param=ref;
  model resp (event='Y') = trt01p strat1 strat2/covb;
  exact trt01p/estimate=both;
  by _Imputation_;
run;
```

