10.1. Changes to Protocol-Defined Analyses

- The FAS will be used to replace ITT in evaluation of the efficacy during DB period. The participants with only baseline but not any postbaseline assessments are excluded from the FAS. Those participants are not considered to be able to contribute to the efficacy analysis because of missing data in postbaseline visits.
- Multiple imputation will be used to replace the NRI to handle missing values in the analysis for primary and key secondary endpoints. Multiple imputation is able to provide unbiased estimates of the parameters under MAR.
- DLQI/CDLQI have been moved from exploratory endpoints to secondary endpoints.

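### Does SAP 7.4 leave VNS response at Week 24 without a usable imputation model?

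*SAP*

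**What the plan says.** SAP 4.1.4 puts VNS response under MI assuming data are missing at random, in the same list as the VASI responses: "For response endpoints, including F-VASI75, F-VASI50, F-VASI90, T-VASI50, and VNS 4 or 5 as listed in the primary and key secondary endpoints". SAP 10.1 records the departure from the protocol: "Multiple imputation will be used to replace the NRI to handle missing values in the analysis for primary and key secondary endpoints".

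For the analysis itself, SAP 7.4 offers only this: "The statistical comparisons for binary outcomes (F-VASI50/90, T-VASI50, and VNS response) will be analyzed using the similar method as specified in the primary analysis".

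The one imputation model written out is in SAP 7.3.1. It is "A regression model including treatment group, stratification factors, and baseline and postbaseline F-VASI scores up to Week 24", fitted by fully conditional specification with 10 imputations. F-VASI75 is derived after the score has been imputed. In the example code only treatment and the two strata are class variables, so the scores are imputed as numbers.

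VNS is a five-level rating that asks: "Compared with before treatment, how noticeable is the vitiligo now" (SAP 7.2.5.1). Scores of 4 or 5 count as success. Protocol Table 3 schedules it at Week 12 and Week 24 (EOT1), with nothing at Day 1 or Weeks 4, 8 and 18.

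**The concern.** The protocol counted missing responses as nonresponse, which needs no model. The SAP's MI needs one, and the 7.3.1 variable list cannot be used for VNS as it stands. SAP 7.4 does not name the variable to impute, the model type, the predictors or the cut rule. The population makes this more than a formality: "All participants who are randomized and have baseline and any postbaseline assessments constitute the FAS". A participant with an early F-VASI and no VNS can therefore be included. The nonresponder, last-observation and tipping-point analyses in SAP 7.3.3 are written for the primary endpoint only.

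SAP 7.4 calls VNS response binary, so someone might impute the yes/no response by ordinary logistic regression. At the planned 1% vehicle rate there will often be no observed vehicle responder. The treatment coefficient is then not finite, and imputed values for missing vehicle participants are close to arbitrary.

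VNS is fifth in the fixed sequence and F-BSA sixth, and SAP 3.2 states: "The endpoint will be tested only if the primary endpoint (and the secondary endpoints in previous steps) are rejected". A few spurious vehicle responders could therefore cost both endpoints.

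**Working it through.** **Inputs.** SAP Table 2, row "Vitiligo - VNS Response at Week 24": 10% active, 1% vehicle, stated power 88%, Fisher's exact test, two-sided 0.05. About 300 participants at 2:1, so 200 and 100. The documents give no missing rate, so 5%, 10% and 20% are assumed.

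**The plan's own figure.** Pooled normal approximation:
- Pooled rate = (200 × 0.10 + 100 × 0.01)/300 = 0.07.
- Null SE = √(0.07 × 0.93 × (1/200 + 1/100)) = 0.03125.
- Alternative SE = √(0.09/200 + 0.0099/100) = 0.02343.
- z = (0.09 − 1.96 × 0.03125)/0.02343 = 1.227, so power is 89.0%.

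Exact enumeration of Fisher's test gives 92.0%. The stated 88% is not optimistic.

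**How often no vehicle responder is observed** (observed number n, rate p): (1 − p)^n.
- p = 1%: 0.99^100 = 36.6%; 0.99^90 = 40.5%; 0.99^80 = 44.8%.
- n = 90: 0.98^90 = 16%; 0.97^90 = 6%; 0.95^90 = 1%.

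**How few vehicle responders matter** (Fisher, 200:100). With 0, 1, 2, 3 or 4 vehicle responders, the active arm needs 9, 13, 16, 20 or 22. At the planned 20 active responders, 3 on vehicle is significant (p = 0.037) and 4 is not (p = 0.075). The margin widens with a better response: 30 active against 6 vehicle gives p = 0.024, and 40 against 10 gives p = 0.032.

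**What the unpenalised binary model would do.** Take 10% missing, with arm and strata as predictors. When no vehicle responder was observed, simulation imputed response to about 50% of the missing vehicle participants; otherwise the rate was about 2.4%. Expected vehicle responders per 100 = 90 × 0.01 + 10 × (0.405 × 0.50 + 0.595 × 0.024) = 0.9 + 2.0 + 0.1 = 3.1 after rounding (exactly 3.07), against a true 1.

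**The readings compared.** Simulated trials, 600 per setting, 10 imputations, true rates 10% and 1%. Power uses the median Fisher p over imputations; complete-data power was 92-93%. Ranges cover different assumptions about dropout and the shape of the VNS categories.

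| Imputation | Result | 5% missing | 10% missing | 20% missing |
|---|---|---|---|---|
| Score, normal draws, cut at 4 | active | 9.6-10.0% | 9.3-10.0% | 8.6-10.1% |
| Ordinal logistic with F-VASI | vehicle | 1.0-1.1% | 0.9-1.1% | 0.9-1.2% |
| | power | 92-93% | 90-93% | 89-94% |
| Binary, augmented likelihood | vehicle | 1.1-1.2% | 1.2-1.4% | 1.4-1.9% |
| Binary, unpenalised, up to 25 Newton steps | vehicle | 2.1-2.7% | 3.3-4.3% | 6.6-8.0% |
| | power | 69-77% | 65-67% | 51-57% |
| Same, stopped at 8 steps | vehicle | 1.4-1.7% | 1.9-2.5% | 3.2-4.2% |
| | power | 91-92% | 89-90% | 84-85% |

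For the score reading the vehicle rate was 0.8-1.1% throughout. A separate run of it gave active 9.2%, vehicle 0.9%, and power 90% against 93% with complete data. Leaving F-VASI out of the ordinal model, when dropout depends on F-VASI, moves the active rate from 10.0% to 10.3-10.4% at 10% missing.

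**Which reading the SAP supports.** SAP 7.3.1 imputes the score and then derives the response. SAP 7.5.1.2 does the same for VASI at Week 52. SAP 7.4 imputes F-BSA by the same MI method and then derives its percentage change. Listing VNS 4 or 5 as a response endpoint does not point to imputing a yes/no variable: SAP 4.1.4 lists F-VASI75 in the same way, and SAP 7.3.1 imputes that as a score. For T-VASI50 and F-BSA the method already has to be carried over by substituting the endpoint's own measure. For VNS the substitution is the 1 to 5 rating at Weeks 12 and 24.

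**The case for a change.** The strongest opposing case is that a type I error-controlled endpoint should have its model named before unblinding, and that VNS is the one key secondary endpoint that does not fit the written template. It adds that a result which changes with the point at which fitting stops shows why the model should be named. Phase 2 also gives some reason to expect sparse vehicle data: the protocol reports 0% vehicle response for F-VASI75 and T-VASI50 at Week 24. A true vehicle rate below 1% would make an empty cell more likely still.

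Much of this stands. The detail is missing, and naming the model would be tidy. The binary failure is also real, in about four trials in ten at the planned rate. What does not follow is that the plan leads there. The harmful model appears nowhere in the SAP and departs from its order of imputing first and deriving afterwards. Where it breaks down, the fit fails to converge, so an analyst would see it. Its size also depends heavily on the iteration limit.

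The simulations lean towards more missing information than the plan implies. They ignore VNS at EOT1, although Protocol 7.1.2 and 8.7 ask for that visit on discontinuation and Table 3 includes VNS in it.

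**Conclusion.** This is a gap in detail that analysts fill sensibly by following the SAP's own template. Imputing the 1 to 5 rating and deriving 4 or 5 gives rates close to the true 10% and 1%. In the separate run the cost was about 3 points of power (90% against 93%), with the active rate pulled slightly down rather than up. An ordinal model does at least as well. No figure in the SAP is wrong, and no conclusion in favour of the drug is made easier.

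This rests on assumed missing rates of 5-20%, where the protocol says only that Phase 2 discontinuation was low. It also rests on Fisher's test with a median-p rule, because the SAP does not say how exact results are combined; the imputed rates do not depend on that rule. The imputed score is cut at 4 without rounding, as SAP 7.3.1 handles F-VASI; a rounded version was not examined. If the yes/no response were imputed without penalisation, the conclusion would not hold at a vehicle rate near 1%.

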7.5. Analysis of Other Secondary Efficacy Parameters

7.5.1. Other Secondary Efficacy Analysis

All other secondary efficacy analyses will be conducted based on the FAS population during the treatment period (double-blind and treatment extension periods).

7.5.1.1. Continuous Efficacy Endpoints

By-visit summary statistics for the following continuous measurements, including actual measurement, change from baseline, and percentage change from baseline, will be presented:

- F-VASI/T-VASI
- F-BSA/T-BSA
- DLQI (or CDLQI) Total score and Subscores

Summary statistics, including sample size, mean, median, standard deviation, minimum, maximum, first quartile, third quartile, and 95% CI, will be presented by visits. A mixed-effect model with repeated measurements may be fit for the comparisons between 1.5% BID cream group and vehicle cream group.

7.5.1.2. Categorical Efficacy Endpoints

For the following categorical parameters, summary statistics, including sample size, frequency, and percentages, will be presented by visit. Similar exact logistic regression models as specified in the primary and key secondary analysis will be used if applicable.

- Proportion of participants achieving F-VASI25/50/75/90
- Proportion of participants achieving T-VASI25/50/75/90
- Proportion of participants in each category of VNS

Secondary endpoint analyses at Week 52 on VASI (eg, F-VASI25/50/75/90 and T-VASI25/50/75/90) will be performed in the FAS population with the following methods:

- For participants randomized in the vehicle group, VASI score at Week 52 in treatment extension period will be imputed using linear extrapolation method based on their data up to Week 24. For participants who discontinue the study drug before Week 24 due to any reason, all missing values of VASI will be imputed using the MI until Week 24 before the extrapolation.
- For participants randomized in the 1.5% BID group, VASI scores at Week 52 will be used for comparison. If the VASI score at Week 52 is missing, the value will be imputed using the MI method based on the data from Day 1 to Week 52.

In each scenario of missing value imputation, the binary outcomes on responses, VASI25/50/75/90, will be derived based on the imputed values. The statistical comparisons for these endpoints will be analyzed using the similar method as specified in the primary analysis.

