4. STUDY DESIGN

4.1. Overall Design

This is a randomized, vehicle-controlled study in adolescent and adult participants (age ≥ 12 years) with non-segmental vitiligo who have depigmented area including $\geq 0.5\%$ BSA on the face, ≥ 0.5 F-VASI, $\geq 3\%$ BSA on nonfacial areas, ≥ 3 T-VASI, and for whom total body involved vitiligo area (facial and nonfacial) does not exceed 10% BSA. Approximately 300 participants will be randomized 2:1 to receive initial study treatment (ruxolitinib cream 1.5% BID:vehicle) for 24 weeks (see [Figure 1](#)). Participants will be stratified by region (North America or Europe) and skin type (Fitzpatrick scale Type I and II vs Type III, IV, V, and VI). Adolescents (≥ 12 to < 18 years) will make up at least 10% of the study population, and no more than 50% of participants will be > 40 years old.

During the double-blind, vehicle-controlled period, participants will receive ruxolitinib cream 1.5% BID or vehicle for 24 weeks to be applied to depigmented areas only on the face and body up to 10% total BSA. Participants should continue to treat depigmented areas identified for treatment at baseline even if the area begins to improve or fully repigment.

After completion of the Week 24 assessments, participants will be offered the opportunity to continue in the treatment extension period. Participants initially randomized to vehicle will be crossed over to active drug, and participants treated with ruxolitinib cream will receive an additional 28 weeks of treatment with ruxolitinib cream 1.5% BID. To be eligible for the treatment extension, participants must have completed the baseline and Week 24 visit assessments, be compliant with study procedures, and not have any safety issues. During the treatment extension, participants should continue to treat depigmented areas identified for treatment at baseline even if the area begins to improve or fully repigment. Total treated areas (facial and nonfacial areas) should not exceed to 10% BSA.

Safety endpoints, such as nature of AEs (type, frequency, and severity), vital signs, targeted physical examination, and routine laboratory investigations, will be monitored and recorded throughout the course of this study.

Following the last application of ruxolitinib cream at Week 52, there will be a 30-day safety follow-up period to evaluate safety and duration of response.

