8.8. Safety Follow-Up

For participants who do not participate in a separate extension study, the safety follow-up period is the interval between the EOT visit (EOT1 or EOT2 depending on the study period when the participant discontinues) and the scheduled safety follow-up visit, which should occur 30 (+ 7) days after the EOT visit (or after the last dose of study drug/treatment if an EOT visit was not performed).

Adverse events and SAEs must be reported up until at least 30 days after the last dose of study drug/treatment, the date of the safety follow-up visit, or until toxicities resolve, return to baseline, or are deemed irreversible, whichever is longer. Reasonable efforts should be made to have the participant return for the safety follow-up visit and report any AEs that may occur during this period.

9. ADVERSE EVENTS: DEFINITIONS AND PROCEDURES FOR RECORDING, EVALUATING, FOLLOW-UP, AND REPORTING

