10.3.1.3. Secondary Analysis

All other secondary and exploratory efficacy variables will be summarized using descriptive statistics. For categorical measurements, summary statistics will include sample size, frequency, and percentages. Similar exact logistic regression models as specified in the primary and key secondary analysis will be used if applicable. For continuous measurements, summary statistics will include sample size, mean, median, SD, standard error of the mean, minimum, and maximum. Continuous efficacy endpoints, including the actual measurement, change from baseline, and percentage change from baseline may also be analyzed by the mixed effect model with repeated measurement.

Secondary endpoint analyses at Week 52 on VASI (eg, F-VASI25/50/75/90 and T-VASI25/50/75/90) will be performed in the ITT population with the following methods:

- Participants who discontinue the study drug before Week 24 due to any reason will be defined as nonresponders for subsequent visits until Week 52.
- For participants who completed Week 24 in the vehicle and 1.5% BID group, missing values of VASI in treatment extension period (including Week 52) will be imputed using linear extrapolation method. The binary outcomes on responses, VASI50/75/90, will be derived based on the imputed values. The statistical comparisons for these endpoints will be analyzed using the similar method as specified in the primary analysis.

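### For participants who stop study drug before Week 24, the SAP replaces the Protocol's Week 52 nonresponder rule with imputation, does not declare the change, and plans no Week 52 check

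*SAP*

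**What the plan says.** Section 10.3.1.3 of the current Protocol (Amendment 3-US-CA, on which SAP 2.1 says the SAP is based) has two rules for the Week 52 VASI responses, and both apply to both arms.

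- Stopped before Week 24: "Participants who discontinue the study drug before Week 24 due to any reason will be defined as nonresponders for subsequent visits until Week 52".
- Completed Week 24: "missing values of VASI in treatment extension period (including Week 52) will be imputed using linear extrapolation method".

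SAP 7.5.1.2 handles the same endpoints by arm.

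- 1.5% BID: the observed Week 52 score is used. Otherwise, "If the VASI score at Week 52 is missing, the value will be imputed using the MI method based on the data", meaning all visits through Week 52. No exception is made for stopping study drug.
- Vehicle: Week 52 is extrapolated linearly from data up to Week 24. For those who stopped before Week 24, "all missing values of VASI will be imputed using the MI until Week 24 before the extrapolation".

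On departures from the Protocol, SAP 10.1 says: "Multiple imputation will be used to replace the NRI to handle missing values in the analysis for primary and key secondary endpoints". In both current documents the Week 52 VASI responses are other secondary endpoints, so this entry does not reach them. Nonresponder imputation, LOCF and the tipping point analysis all sit in SAP 7.3.3, which covers the primary Week 24 endpoint. The one tipping point table in SAP Appendix A is also for Week 24.

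**The concern.** A participant who stops the active cream before Week 24 is a certain nonresponder at Week 52 under the Protocol and a possible responder under the SAP. What the imputation model can learn from decides how likely that response is.

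After permanent discontinuation, the Protocol schedules an EOT visit (7.1.2, 8.7) and then a safety follow-up visit, "which should occur 30 (+ 7) days after the EOT visit". There is no Week 52 visit for someone who stopped. To enter the extension, "participants must have completed the baseline and Week 24 visit assessments, be compliant with study procedures, and not have any safety issues". Active-arm scores from Week 28 to Week 52 therefore come almost entirely from people still applying cream. MI fitted to those data estimates a rate close to the one expected had all participants continued, and the SAP does not name that as its target.

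The Week 52 active response rate is the study's main evidence on longer treatment. A reader who has the Protocol would take it to count early stoppers as failures.

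**Working it through.** **The plan's own figure.** The current Protocol and SAP state no response rate or power for Week 52. Their power tables cover Week 24 only. The primary row (20% vs 5%, 200:100, Fisher's exact test, two-sided 0.05) recomputes to 96.6% or 95.8%, depending on how the two-sided p-value is defined, against 95% stated. That confirms the allocation used below but does not bear on this point.

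**Inputs.**
- Active arm: 300 × 2/3 = 200 (SAP 3.3).
- Phase 2 Week 52 rates for 1.5% BID: F-VASI75 51.5% and T-VASI50 36.4% (Protocol 2.4.2.2.3). These are taken as the rate r that MI would return.
- Share d of the active arm stopping before Week 24: not given, so assumed at 5%, 10%, 15% and 20%. Protocol 2.4.2.2.3 says only that Phase 2 discontinuation through 52 weeks was low.

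**Direction.** Nonresponse is the lowest value a binary response can take. For those who stopped before Week 24, replacing it with an imputed value can only leave the active rate unchanged or raise it.

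**Size, if stopping is unrelated to outcome.** MI rate = r. Protocol-rule rate = r × (1 − d). Gap = r × d. For example, 51.5% × 10% = 5.15 points, or 0.0515 × 200 ≈ 10 participants.

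| d | F-VASI75, Protocol rule | Gap (points) | Extra responders of 200 | T-VASI50, Protocol rule | Gap (points) |
|---|---|---|---|---|---|
| 5% | 48.9% | 2.6 | 5 | 34.6% | 1.8 |
| 10% | 46.4% | 5.2 | 10 | 32.8% | 3.6 |
| 15% | 43.8% | 7.7 | 15 | 30.9% | 5.5 |
| 20% | 41.2% | 10.3 | 21 | 29.1% | 7.3 |

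**Simulation check.** There were 200 active participants and 150 replicates, with sequential-regression MI and 10 imputations. Stopping came after Week 8, 12 or 18, and the true on-treatment Week 52 response was set near 50%. The data model is assumed, not taken from the documents.

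| d | Random stopping: MI | Protocol rule | Gap (points) | Early poor responders stop more: MI | Protocol rule | Gap (points) |
|---|---|---|---|---|---|---|
| 5% | 50.1% | 47.8% | 2.4 | 50.9% | 49.0% | 1.8 |
| 10% | 50.1% | 45.1% | 5.0 | 50.6% | 47.0% | 3.6 |
| 15% | 50.4% | 42.7% | 7.6 | 49.9% | 44.6% | 5.3 |
| 20% | 50.5% | 40.5% | 10.0 | 50.6% | 43.6% | 7.0 |

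MI returned about 50-51% however many stopped, which is the rate with everyone treated for 52 weeks. When early poor responders stop more often, the gap shrinks but does not vanish.

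**Between-arm difference.** The SAP also drops the nonresponder rule for vehicle participants. The change in the difference is therefore r(active) × d(active) − r(vehicle) × d(vehicle). It is smaller than the active-arm gap whenever some vehicle stoppers are imputed as responders.

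**The case against.** The other side has a good deal to say. Protocol 10.3 leaves missing-data procedures to the SAP, and SAP 7.5.1.2 states its method openly. MI under missing at random aims at a recognised on-treatment quantity, and FAS names a population, not an estimand. The model also conditions on each participant's own scores, so a poor early responder is drawn from a poor trajectory and is not simply handed a stayer's result. The FAS excludes those with no postbaseline assessment, so the very earliest dropouts are never imputed. SAP 7.3.1 makes rescue-therapy users nonresponders, and the instruction to use a similar method may carry that to Week 52. All of this stands. It makes MI defensible as the main method and can reduce the gap, but it neither declares the change nor supplies a check.

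A reader might also infer stronger points that the documents do not support.

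- *Participants barred from the extension, or stopping during it, are also inflated relative to the Protocol.* For anyone who completed Week 24, the Protocol itself imputes, by linear extrapolation. MI has not been shown to give a higher rate than that.
- *The gap applies to every missing Week 52 score.* That compares MI with a nonresponder rule for all missing data, which neither document contains. If 10-20% lacked a score and, as an assumption, half of them had stopped before Week 24, the F-VASI75 gap would be 2.6-5.2 points, not 5.2-10.3.
- *The treatment comparison is biased by the full active-arm gap.* Vehicle stoppers lose the nonresponder rule too.
- *Nothing planned would reveal the problem.* SAP 6.2 tabulates discontinuations by reason in both periods, so the extent of stopping will be visible. Its effect on the Week 52 rate will not.

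**Conclusion.** The point holds for participants who stop study drug before Week 24. The two documents give them different Week 52 outcomes, and SAP 10.1 does not say so. It also does not mention that MI replaces the Protocol's linear extrapolation for active participants who completed Week 24. No Week 52 sensitivity analysis is planned.

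For the early stoppers the direction is certain. The size rests on an assumed dropout: the table's ranges are for 5-20% stopping before Week 24, with stopping unrelated to outcome and the Phase 2 rates carried over. The low Phase 2 discontinuation makes the lower end likelier. The Week 52 endpoints lie outside the fixed sequence in SAP 3.2, so no alpha-controlled conclusion changes. This is a worthwhile, inexpensive improvement in how the longer-term rate is reported. It does not threaten the primary result.

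**What to change.** 1. In SAP 7.5.1.2, add a Week 52 analysis of F-VASI25/50/75/90 and T-VASI25/50/75/90 beside the MI analysis. In it, participants in either arm who stopped study drug before Week 24 are nonresponders, as Protocol 10.3.1.3 states. Leave the handling of everyone else as in the MI analysis, so that the contrast isolates this rule.
2. In SAP 10.1, list the Week 52 changes: the nonresponder rule dropped for those who stopped before Week 24, and MI in place of linear extrapolation for active participants who completed Week 24.
3. Tabulate the number of imputed Week 52 values by arm and reason.

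Counting participants who do not enter the extension, or who stop during it, as nonresponders goes beyond the Protocol. Offer it only as a further sensitivity analysis.

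The cost is some SAP wording, one extra analysis and one table. A somewhat lower active rate will appear beside the main one. Study conduct does not change.
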